9.5.1.5.4 VITAL SIGNS AND WEIGHT MEASUREMENTS

Vital sign measurements (ie, systolic and diastolic BP [mmHg], pulse [beats per minute], respiratory rate [per minute], body temperature [in centigrade]), and weight (kg) will be obtained as designated in the Schedule of Procedures/Assessments (Table 2) by a validated method. BP and pulse will be measured after the subject has been sitting for 5 minutes. All BP measurements should be performed on the same arm, preferably by the same person.

When vital signs are to be obtained concurrently with PK or other blood samples, the vital sign measurements will be performed before drawing blood samples in order to maximize the accuracy of blood sampling times while minimizing the potential effects of blood drawing on recordings obtained during safety assessments.

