9.5.2 Schedule of Procedures/Assessments

9.5.2.1 Schedule of Procedures/Assessments

[Table 2](#) presents the Schedule of Procedures/Assessments for the study.

Table 2 Schedule of Procedures/Assessments in Study APD356-A001-403

Phase:	Prerandomization ^a		Randomization										Other		
Period:	Screening		Treatment										Follow-Up		
Visit Number:	1	2 ^a	3	4	5	6	7	8	9	10	11 (EOT)	EOS	Un-scheduled	Early discontinuation	
Day:	-30 to -1	1													
Weeks ^{b,c} :		0	1	5	8	12	20	28	36	44	52	56			
Procedure															
Informed Consent	X														
Demography	X														
Medical History	X														
Prior/concomitant medication assessments	X	X	X	X	X	X	X	X	X	X	X		X	X	
Inclusion/exclusion criteria	X	X													
Physical Examination ^d	X	X	X			X		X			X	X	X	X	
Vital signs	X	X	X	X	X	X	X	X	X	X	X	X	X	X	
Height	X	X	X	X	X	X	X	X	X	X	X	X	X	X	
Weight	X	X	X	X	X	X	X	X	X	X	X	X	X	X	
Waist circumference	X	X		X		X		X	X		X	X	X	X	
Routine clinical laboratory tests	X	X	X	X		X		X			X	X	X	X	
Urinalysis	X		X	X		X		X	X		X	X	X	X	
Urine drug and cotinine test	X														
Fasting plasma glucose, Fasting Insulin, HOMA-IR, and HbA _{1c} sampling	X	X				X		X			X			X	
T4 and TSH	X							X			X			X	
AM serum cortisol		X									X				
Testosterone, Estradiol	X						X				X				

Table 2 Schedule of Procedures/Assessments in Study APD356-A001-403

Phase:	Prerandomization ^a		Randomization									Other		
Period:	Screening		Treatment									Follow-Up		
Visit Number:	1	2 ^a	3	4	5	6	7	8	9	10	11 (EOT)	EOS	Un-scheduled	Early discontinuation
Day:	-30 to -1	1												
Weeks ^{b,c} :		0	1	5	8	12	20	28	36	44	52	56		
Procedure														
Pregnancy test (Urine)	X	X	X	X	X	X	X	X	X	X	X	X		
Randomization		X												
IxRS	X	X		X	X	X	X	X	X	X	X			
Study drug dispensing		X		X	X	X	X	X	X	X			X	
Collect study medication				X	X	X	X	X	X	X	X	X	X	X
Drug accounting and compliance			X	X	X	X	X	X	X	X	X		X	X
AE monitoring	X	X	X	X	X	X	X	X	X	X	X	X	X	X
ECG		X						X			X	X		X
Echocardiograph	X ^f							X			X			X
CDC growth chart	X	X		X		X		X	X		X	X	X	X
Tanner Staging	X	X						X			X	X	X	X
C-SSRS		X	X	X	X	X	X	X	X	X	X	X	X	X
WRAML-2		X		X				X			X	X		X
PHQ-9		X	X	X		X	X		X		X	X		X
Hand x-ray for bone age		X				X		X			X			X
OC, PICP, and Hydroxy-proline		X						X			X			X
Urine NTX		X						X			X			
PK/PD blood sampling						X		X	X		X			X

Table 2 Schedule of Procedures/Assessments in Study APD356-A001-403

Phase:	Prerandomization ^a		Randomization										Other		

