Period:	Screening		Treatment										Follow-Up		
Visit Number:	1	2 ^a	3	4	5	6	7	8	9	10	11 (EOT)	EOS	Un- scheduled	Early discon- tinuation	
Day:	-30 to -1	1													
Weeks ^{b,c} :		0	1	5	8	12	20	28	36	44	52	56			
Procedure															
Prolactin	X							X			X			X	
Standardized age-appropriate lifestyle modification counseling ^e		X	X	X	X	X	X	X	X	X			X		

AE = adverse event, AM = morning; CDC = Centers for Disease Control and Prevention, C-SSRS = Columbia-Suicide Severity Rating Scale, ECG = electrocardiogram, EOS = End of Study, EOT = End of Treatment, HbA_{1c} = hemoglobin A1c, HOMA-IR = Homeostatic Model Assessment of Insulin Resistance, IxRS = interactive voice or web response system, NTX = N-telopeptide, OC = osteocalcin; PHQ-9 = The Patient Health Questionnaire, PICP = carboxyterminal propeptide of type I procollagen, PK = pharmacokinetics, T4 = thyroxine, TSH = thyroid stimulating hormone, WRAML-2 = Wide Range Assessment of Memory and Learning-2.

^a: Baseline measurements will be collected on Day 1, before drug administration unless specified otherwise.

^b: Window ± 7 days for all visits after Visit 2 except for Weeks 12 and 28 (the window for these visits will be broader at ± 14 days). Week is shown unless otherwise indicated.

^c: On the day of the Week 12, 28, and 52 clinic visits, subjects will take their morning dose of study drug on the day before their scheduled clinic visit. On the day of the clinic visit, subjects will be instructed to take their study drug at approximately the same time as the morning before, with no additional doses taken that day. Two blood samples for determination of plasma concentrations of lorcaserin will be taken: predose (within 30 minutes before dosing) and within 1 to 3 hours after dosing. On the day of the Week 36 clinic visit, subjects will take the morning dose at home, and 1 blood sample for determination of plasma concentrations of lorcaserin will be collected at the investigational site within 4 to 6 hours after dosing. Dose times **must** be recorded for the last 2 dosing times prior to the clinic visit.

^d: Includes a neuromuscular assessment

^e: Lifestyle modification counseling will also be performed at Weeks 3, 24, 32, 40, and 48 in addition to counseling at the scheduled visits in [Table 2](#).

^f: Echocardiographic assessments will be performed during screening period after subjects have met all other inclusion and exclusion criteria.

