9.5.2.3 Total Volume of Blood Sampling

[Table 3](#) presents the number of blood samples and the total volume of blood that will be collected throughout the study. Additional samples may be taken at the discretion of the investigator if the results of any tests fall outside reference ranges or clinical symptoms necessitate testing to ensure subject safety.

Table 3 Summary of Blood Sample Volumes

	Sample Volume per Collection (mL)	Number of Collection Time Points	Total Volume Collected (mL)
Clinical laboratory tests	12	Screening: 1 Visits 2, 3, 4, 6, 8; 11/EOT, EOS	12×8=96
T4, TSH, Cortisol, Testosterone, estradiol, Serum OC and PICP, Hydroxy-proline; Fasting prolactin levels	10	Screening: 1 Visits 8; 11/EOT/Early discontinuation	10×3=30
Prolactin, FPG, Insulin, and HbA _{1c} sampling	4	Screening: 1 Visits 2, 6, 8; 11/EOT/Early discontinuation	4×5=20
PK/PD blood sampling	4	Visits 6, 8, and 11/EOT/Early discontinuation (2 samples each); Visit 9 (1 sample only)	7×4=28
Total			174

EOS = End of Study; EOT = End of Treatment; FPG = fasting plasma glucose; HbA_{1c} = hemoglobin A_{1c}; OC = osteocalcin; PD = pharmacodynamic; PICP = carboxyterminal propeptide of type I procollagen; PK = pharmacokinetics; T4 = thyroxine; TSH = thyroid stimulating hormone.

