9.7.1.1.2 SECONDARY EFFICACY ENDPOINTS

KEY SECONDARY ENDPOINT

- Proportion (%) of subjects achieving at least a 5% BMI reduction at Week 52

OTHER SECONDARY ENDPOINT

- Proportion (%) of subjects achieving at least a 5% BMI reduction at Week 12
- Proportion (%) of subjects achieving at least a 10% BMI reduction at Week 52
- Percentage change in BMI from Baseline to Week 52
- Change and percentage change in BMI from Baseline to Week 52 and proportion (%) of subjects achieving at least a 5% or 10% BMI reduction at Week 52 by the outcome of achieving at least a 5% BMI reduction at Week 12
- Change in waist circumference from Baseline to Week 52
- Change in HbA_{1c} from Baseline to Week 52
- Change in fasting glucose, fasting insulin, and HOMA-IR from Baseline to Week 52
- Change in BP (systolic and diastolic) and heart rate from Baseline to Week 52

- Change in fasting lipid profile (total cholesterol, LDL cholesterol, HDL cholesterol, triglycerides) from Baseline to Week 52
- Proportion (%) of subjects with prehypertension or primary hypertension at Week 52
- Proportion (%) of subjects with dyslipidemia at Week 52

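### The Screening values of BP, heart rate, waist, glycemic measures and lipids have no stated role in the analysis of the continuous change-from-baseline secondary endpoints, where they could add a modest, nearly free gain in precision

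*Protocol*

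**What the plan says.** This concerns the current version of the protocol (ages 12 to 17).

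- **Two pre-dose measurements.** Section 9.5.2.1, Table 2, marks both Visit 1 (Day -30 to -1) and Visit 2 (Day 1) for vital signs ("Vital signs X X"), for waist ("Waist circumference X X"), for routine laboratory tests, and for the row that begins "Fasting plasma glucose, Fasting Insulin, HOMA-IR, and HbA". Section 9.5.1.5.4 places BP and pulse among the vital signs, and Table 1 places the lipids in the laboratory panel. Table 3 (section 9.5.2.3) lists the glucose, insulin and HbA1c draws as "Screening: 1 Visits 2, 6, 8; 11/EOT/Early discontinuation", so two of them precede dosing.
- **Baseline.** Footnote a to Table 2: "Baseline measurements will be collected on Day 1, before drug administration unless specified otherwise". Nothing in the current version specifies otherwise for these measures.
- **Endpoints.** Section 9.7.1.1.2 defines the continuous cardiometabolic endpoints as changes, for example "Change in BP (systolic and diastolic) and heart rate from Baseline to Week 52". Waist, HbA1c, glucose, insulin, HOMA-IR and fasting lipids are listed in the same form. Prehypertension or hypertension, and dyslipidemia, are listed as proportions at Week 52.
- **Analysis.** Section 9.7.1.6 assigns MMRM to the continuous secondary endpoints without naming their covariates.

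**The concern.** Several of these measures fluctuate between visits for reasons unrelated to treatment. A single Day 1 value then carries noise that a second pre-randomization value would partly remove, and that second value is already scheduled and collected. The eligibility criteria make no use of insulin, HOMA-IR or waist, so their Screening values have no stated purpose at all. For BP, exclusion criterion 22 itself asks for two readings on two days, while the change endpoint refers back to one baseline visit.

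What is at stake is the width of the confidence intervals for the glycemic, BP, lipid and waist changes. The protocol states no power for these endpoints, and with the assumed 40% dropout only about 216 of 360 subjects would be evaluable.

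**Working it through.** **The plan's own figures.** The protocol gives no SD or power for any cardiometabolic endpoint, so there is none to reproduce here. Its BMI figures do reproduce. With 180 × 0.6 = 108 evaluable per arm, a difference of 1 kg/m² and SD 2.2, the t-test has 91.4% power (stated: at least 90%). Fisher's exact test at 20% versus 40% has 87.1% (stated: greater than 85%). Neither depends on this point.

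**Inputs assumed, because the protocol gives none.** r is the correlation of each pre-dose value with Week 52. rb is the correlation of Screening with Day 1.

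**Formulas** (unit variance, Week 52 comparison, complete data):

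- One baseline covariate: residual variance 1 − r².
- Two baselines, entered separately or as their mean: 1 − 2r²/(1 + rb).
- Unadjusted change score: 2(1 − r) from one baseline, 1 + (1 + rb)/2 − 2r from the mean of two.

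Example with rb = 0.8 and r = 0.5: 1 − 0.25 = 0.750 falls to 1 − 0.50/1.8 = 0.722, a reduction of 3.7%.

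| rb | r | One baseline | Two baselines | Reduction | 80% power becomes | Reduction, unadjusted change |
|---|---|---|---|---|---|---|
| 0.5 | 0.5 | 0.750 | 0.667 | 11.1% | 84.4% | 25% |
| 0.7 | 0.7 | 0.510 | 0.424 | 17.0% | 86.7% | 25% |
| 0.8 | 0.8 | 0.360 | 0.289 | 19.8% | 87.8% | 25% |
| 0.8 | 0.7 | 0.510 | 0.456 | 10.7% | 84.2% | 16.7% |
| 0.8 | 0.5 | 0.750 | 0.722 | 3.7% | 81.5% | 10% |
| 0.9 | 0.5 | 0.750 | 0.737 | 1.8% | 80.7% | 5% |
| 0.9 | 0.3 | 0.910 | 0.905 | 0.5% | 80.2% | 3.6% |

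The first three rows set rb = r, which is the favourable case. The two pre-dose values are at most 30 days apart, with no study drug or counseling between them, so rb above r is the more natural expectation. For r between 0.5 and 0.8 and rb up to 0.9, the reduction runs from about 2% to 20%; it is smaller at lower r.

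**How the second value must enter.** If the modelled response is the change from Day 1 and the mean of the two values is the only baseline covariate, the residual variance is 1 − 2r²/(1 + rb) + (1 − rb)/2. At rb = 0.8 and r = 0.5 this is 0.722 + 0.100 = 0.822, which is worse than the 0.750 from Day 1 alone. Entering Day 1 and Screening as two covariates gives 0.722 whether the response is the visit value or its change from Day 1.

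**The case against.** The strongest reply is that the protocol contains no error here. Footnote a says when baseline is collected and carries an exception clause; it says nothing about covariates. Covariates for a secondary MMRM are ordinary SAP content, and a single Day 1 baseline is conventional and valid. All of that stands, and it limits the point to a suggestion. It does not remove it: the proposal is a concrete, more efficient use of data already scheduled, not a request for missing detail.

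Three stronger readings are tempting, and the documents support none of them.

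- A reader might infer that the plan discards the Screening values. It collects them and leaves the SAP free to use them; it simply states no use.
- A reader might infer that every cardiometabolic secondary endpoint loses precision. The Week 52 proportions with prehypertension or hypertension and with dyslipidemia are statuses, not changes from Baseline.
- A reader might expect a reduction of 8% to 17%. That needs Screening and Day 1 to correlate no better with each other than with Week 52, for a common correlation of 0.4 to 0.7. At rb of 0.8 to 0.9 and r of 0.5, it is 2% to 4%.

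Two further objections stand in part. Pre-randomization BP is restricted in range by exclusion criterion 22, which lowers its value as a covariate but leaves it valid. Fasting is explicit for glucose and insulin at both visits but only probable for lipids, because the routine laboratory row does not mention it.

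**Conclusion.** The point holds as an efficiency improvement for the continuous change-from-baseline secondary endpoints only. The expected gain is about 2% to 20% of residual variance, or roughly 1 to 8 points from a nominal 80% power. This rests on assumed correlations and on Screening predicting Week 52 about as well as Day 1 does; if it predicts less well, the gain is smaller. It should be largest for BP, insulin, HOMA-IR and triglycerides and probably small for waist and HbA1c, but that ordering is a judgement about how much each measure varies from visit to visit, not something the protocol states. Validity, the primary and key secondary tests, type I error and sample size are unaffected. Priority is low.

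**What to change.** Keep Day 1 as Baseline for the displayed change. In the MMRM for the continuous cardiometabolic secondary endpoints, include the Day 1 value and add the Screening value as a second baseline covariate. Where Screening is missing, use Day 1 alone, for example by setting the missing covariate to the Day 1 value so that the subject stays in the model. The mean of the two values is an acceptable single covariate only if the modelled response is the visit value or the change from that mean, for the reason shown in the working.

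The cost is one sentence in the SAP, about one degree of freedom against some 216 evaluable subjects, and no new visit or blood draw. The remaining downside is that Screening values can be up to 30 days old, equally in both arms.

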9 INVESTIGATIONAL PLAN

9.1 Overall Study Design and Plan

This is a multicenter, randomized, double-blind, placebo-controlled, parallel-group study in obese adolescents ages 12 to 17 years. Approximately 360 subjects will be randomized in a 1:1 ratio to Belviq XR 20 mg QD (180 subjects) and placebo (180 subjects). Subjects will be stratified by sex. Subjects will receive Belviq XR 20 mg or placebo QD in a 1:1 ratio for up to 52 weeks. Throughout the duration of the study, subjects will be encouraged to adhere to a lifestyle modification program that includes a standardized, age-appropriate diet and exercise counseling (see [Appendix 2](#)).

The study will consist of 2 phases: Prerandomization and Randomization. The Prerandomization Phase will last up to 30 days and consists of 1 visit during which subjects will be screened for eligibility. The Randomization Phase consists of a Treatment Period and a Follow-Up Period. The Treatment Period will last for a maximum of 52 weeks, with visits at Weeks 1, 5, 8, 12, 20, 28, 36, 44, and 52; the Follow-Up Period will extend from the End of Treatment (EOT) visit to the End of Study (EOS) visit.

Subjects who screen fail can be re-screened only once after 60 days. All subjects will continue in the study until the 52-week evaluation is completed. Subjects who discontinue treatment prematurely will be followed up until study completion.

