9.5.1.5.1 ADVERSE EVENTS AND EVENTS ASSOCIATED WITH SPECIAL SITUATIONS

An AE is any untoward medical occurrence in a patient or clinical investigation subject administered an investigational product. An AE does not necessarily have a causal relationship with the medicinal product. For this study, the study drug is Belviiq XR (lorcaserin hydrochloride).

The criteria for identifying AEs in this study are:

- Any unfavorable and unintended sign (including an abnormal laboratory finding), symptom, or disease temporally associated with the use of an investigational product, whether or not considered related to the investigational product (Note: Every sign or symptom should not be listed as a separate AE if the applicable disease [diagnosis] is being reported as an AE)
- Any new disease or exacerbation of an existing disease
- Any deterioration in non-protocol-required measurements of a laboratory value or other clinical test (eg, ECG, x-ray) that results in symptoms, a change in treatment, or discontinuation of study drug
- Recurrence of an intermittent medical condition (eg, headache) not present pretreatment (Baseline)
- An abnormal laboratory test result should be considered an AE if the identified laboratory abnormality leads to any type of intervention, withdrawal of study drug, or withholding of study drug, whether prescribed in the protocol or not.

All AEs observed during the study will be reported on the Adverse Event CRF. All AEs, regardless of relationship to study drug or procedure, should be collected beginning from the time the subject signs the study ICF through the last visit in the Treatment Phase. Subjects who fail screening primarily due to AE(s) must have the AE(s) leading to screen failure reported on the Screening Disposition CRF. SAEs will be collected for 28 days after the last dose.

Abnormal laboratory values should not be listed as separate AEs if they are considered to be part of the clinical syndrome that is being reported as an AE. It is the responsibility of the investigator to review all laboratory findings in all subjects and determine if they constitute an AE. Medical and scientific judgment should be exercised in deciding whether an isolated

laboratory abnormality should be classified as an AE. Any laboratory abnormality considered to constitute an AE should be reported on the Adverse Event CRF.

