9.5.5 Completion/Discontinuation of Subjects

The investigator may withdraw the subject from the study at any time for safety or administrative reasons. A subject may elect to discontinue the study at any time for any reason. All subjects will continue in the study until the 52-week evaluation is completed. Subjects who discontinue treatment prematurely will be followed up until study completion. All subjects who discontinue the study are to complete the study's early discontinuation procedures indicated in the Schedule of Procedures/Assessments ([Table 2](#)).

The investigator will promptly explain to the subject involved that the study will be discontinued for that subject and provide appropriate medical treatment and other necessary measures for the subject. A subject who has ceased to return for visits will be followed up by mail, phone, or other means to gather information such as the reason for failure to return, the status of treatment compliance, the presence or absence of AEs, and clinical courses of signs and symptoms.

Subjects who discontinue early from the study will be discontinued for 1 of these primary reasons: AE(s), lost to follow-up, subject choice, withdrawal of consent, pregnancy, study terminated by sponsor, or other. In addition to the primary reason, the subject may indicate 1 or more of secondary reasons for discontinuation. Study disposition information will be collected on the Subject Disposition CRF.

Detailed retention strategies will be developed and included in study manual. These include a highly trained and competent staff, easy access to the clinic, reminder and follow-up calls, interactive group sessions with games and hands-on nutrition and physical activity demonstrations, random raffle drawings, social events, birthday and holiday cards, and newsletters. In addition, home visits for assessments of families will be an option, as needed, to maximize data collection. This detailed retention plan will help prevent missing data.

A subject removed from the study for any reason may not be replaced.

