9.7.1.5 Prior and Concomitant Therapy

All investigator terms for medications recorded in the CRF will be coded to an 11-digit character code using the World Health Organization Drug Dictionary. The number (percentage) of subjects who took prior and concomitant medications will be summarized for the Safety Analysis Set by treatment group, Anatomical Therapeutic Chemical class, and World Health Organization Drug Dictionary preferred term (PT). Prior medications will be defined as medications that stopped before the first dose of study drug. Concomitant medications will be defined as medications that started on or after the date of the dosing of study drug and continued up to 30 days afterward.

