9.7.1.8.2 ADVERSE EVENTS

The AE verbatim descriptions (investigator terms from the CRF) will be classified into standardized medical terminology using the Medical Dictionary for Regulatory Activities (MedDRA). Adverse events will be coded to the MedDRA (Version 18.0 or higher) lower level term closest to the verbatim term. The linked MedDRA PT and primary system organ class (SOC) are also captured in the database.

A treatment-emergent AE (TEAE) is defined as an AE that emerges during treatment (up to 28 days after the last dose of study drug), having been absent at pretreatment (Baseline) or

- Reemerges during treatment (up to 28 days after the last dose of study drug), having been present at pretreatment (Baseline) but stopped before treatment, or
- Worsens in severity during treatment relative to the pretreatment state, when the AE is continuous.

Only those AEs that were treatment emergent will be included in summary tables. All AEs, treatment emergent or otherwise, will be presented in subject data listings.

The TEAEs will be summarized by treatment group. The following summaries will be reported for TEAES:

- Incidence of TEAEs in descending order of frequency
- Incidence of TEAEs by SOC and PT
- Incidence of treatment-related TEAEs by SOC and PT
- Incidence of TEAEs by SOC, PT and maximum severity (mild, moderate, or severe)
- Incidence of treatment-related TEAEs by SOC, PT, and maximum severity (mild, moderate, or severe)
- Incidence of TEAEs by SOC, PT, and relationship to study drug (Yes [related] or No [not related])

A subject will be counted only once within a SOC or PT, if the subject experienced more than 1 TEAE within a specified SOC and PT.

The following summaries will also be presented for the treatment-emergent SAEs.

- Incidence of TEAEs leading to death
- Incidence of treatment-emergent SAE by SOC and PT
- Incidence of treatment-related treatment-emergent SAE by SOC and PT

In addition, subjects with TEAEs leading to discontinuation from study drug and AEs of special interest as described in Section 9.5.4.3.2 will be summarized by MedDRA SOC and PT for each treatment group.

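### The End of Study visit is tied to Week 56, not to the last dose, and non-serious AE collection is tied to a visit, so the 28-day treatment-emergent window is not guaranteed to be observed

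*Protocol*

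**What the plan says.** All references are to the current version of the protocol, the one with screening echocardiography. The superseded versions bound behind it are not used.

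- **Visits.** Table 2 in 9.5.2.1 lists the weeks as "0 1 5 8 12 20 28 36 44 52 56", with EOT at Week 52 and EOS at Week 56. Footnote b reads "Window ± 7 days for all visits after Visit 2 except for Weeks 12 and 28", so both visits carry ±7 days. Section 9.1 adds that "the Follow-Up Period will extend from the End of Treatment (EOT) visit to the End of Study (EOS) visit". Nothing ties EOS to the last dose.
- **Last dose.** Footnote c covers the Week 12, 28 and 52 visits: "On the day of the clinic visit, subjects will be instructed to take their study drug". Table 2 dispenses no drug at Week 52.
- **Analysis window.** Section 9.7.1.8.2: "A treatment-emergent AE (TEAE) is defined as an AE that emerges during treatment (up to 28 days after the last dose of study drug".
- **Collection window.** Section 9.5.1.5.1 says that all AEs "should be collected beginning from the time the subject signs the study ICF through the last visit in the Treatment Phase". The same paragraph extends collection to 28 days after the last dose for SAEs only.
- **Leavers.** Section 9.5.5: "All subjects who discontinue the study are to complete the study's early discontinuation procedures indicated in the Schedule of Procedures/Assessments". Table 2 has one Early discontinuation column and nothing after it. Subjects who only stop the drug stay in the study and keep their visits.
- **Concomitant medication.** Section 9.7.1.5 counts medication that "continued up to 30 days afterward". Table 2 marks no medication check at EOS.

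**The concern.** The protocol defines a treatment-emergent event by time since the last dose, but it gathers non-serious events by visit. The two agree only if the final visit falls on or after day 28, and the schedule leaves no margin for that. A new non-serious event that starts after the final visit and before day 28 belongs in the TEAE tables under 9.7.1.8.2, yet no collection rule covers it. The reported TEAE incidence would then be lower than the protocol's own definition implies. The closing scheduled C-SSRS and pregnancy test, both marked at EOS, can also be done before the 28 days are up.

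**Working it through.** **Inputs.** Week 0 is Day 1, so EOT is 52 × 7 = 364 days and EOS 56 × 7 = 392 days after Day 1 (Table 2). Each has ±7 days (footnote b). A completer's last dose is on the EOT day (footnote c). The TEAE window is 28 days (9.7.1.8.2).

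**Nominal gap.** 392 − 364 = 28 days, which matches the TEAE window exactly.

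**Range allowed by the windows.** Gap = (392 + b) − (364 + a) = 28 + b − a, with a and b each from −7 to +7.
- Shortest (a = +7, b = −7): 385 − 371 = 14 days.
- Longest (a = −7, b = +7): 399 − 357 = 42 days.

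**Other readings.**
- EOT exactly at Week 52, or EOS counted from EOT: 28 ± 7, that is 21 to 35 days.
- Last dose the day before EOT: 15 to 43 days.

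None of these readings guarantees 28 days.

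**How often the gap falls short.** The documents do not say how visits spread within their windows. As an illustration only, take whole days, independent and uniform. There are 15 × 15 = 225 combinations. A shortfall of d days arises in 15 − d of them, for d = 1 to 14, and these sum to 105. So 105/225 = 46.7% fall below 28 days. The mean shortfall among them is Σ d(15 − d)/105 = (15 × 105 − 1015)/105 = 560/105 = 5.3 days, and the maximum is 14. If EOS is counted from EOT, 7 of 15 days fall short (also 46.7%), by at most 7 days.

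**Collection rule against analysis rule.** Section 9.1 names only a Prerandomization and a Randomization Phase, so the Treatment Phase in 9.5.1.5.1 has to be interpreted.
- Read as the Treatment Period, collection of non-serious AEs ends at Week 52, on the day of the last dose. It then covers none of the 28 days and conflicts with the AE monitoring that Table 2 marks at EOS.
- Read as the Randomization/Treatment Phase of 9.1.2, which includes follow-up, collection ends at EOS, which may be day 14.

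Neither reading secures the window in 9.7.1.8.2.

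**Subjects who leave the study.** If the Early discontinuation visit falls k days after the last dose (k below 28), 28 − k days have no scheduled contact. The documents do not give k.

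**Subjects who only stop the drug.** They attend through EOS. The earliest EOS is 392 − 7 = 385 days, and 385 − 28 = 357 days is Week 51. Anyone whose last dose is at or before Week 51 therefore has EOS at 28 days or later.

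**The case against.** The strongest reply is that the plan is right as scheduled: Week 52 to Week 56 is 28 days, and Table 2 marks AE monitoring at EOS. Section 9.1 can also be read as counting follow-up from EOT, which narrows the range. Both points stand. They limit the finding to what the visit windows permit, but they do not restore a guarantee.

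The other safeguards are also real. SAEs are collected for 28 days whatever the visit date. AEs are followed for 28 days after the last dose or until resolution. Subjects who stop attending are contacted by mail, telephone or other means, including about AEs (9.5.5). However, follow-up concerns events already known. The contact rule has no timing, and it is written for people who stop coming, not for someone who completes the Early discontinuation visit and leaves.

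Three stronger readings are tempting, and the documents do not support them:

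- **Bias by arm.** A reader might infer that subjects who stop for intolerance go unobserved, mostly on active drug, which would flatter it. Subjects who stop the drug but stay in the study keep their visits, and nothing in the documents shows a loss that differs by arm.
- **144 subjects unobserved.** 40% of 360 is 144, but the 40% is the dropout assumption in 9.7.2. The protocol does not split it between stopping the drug and leaving the study.
- **Pregnancy and suicidality uncovered.** Conceptions within 28 days of the last treatment must be reported (9.5.4.2). Suicidal behavior is always serious, and suicidal ideation is reported through the SAE procedures (9.5.1.5.2, 9.5.4.3.2). Only the timing of the scheduled test and scale is affected.

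**Conclusion.** The concern holds in a limited form. A compliant EOS visit can fall 14 to 42 days after a completer's last dose (21 to 35 if counted from EOT), and the collection rule for non-serious AEs is not aligned with the 28-day TEAE definition. New non-serious events between the final visit and day 28 can be missed, both in completers with an early EOS and in subjects who leave the study. The range follows from Table 2 and its footnotes alone, with the last dose on the Week 52 visit day. The 46.7% rests on assumed independent, uniform visit timing and is not a forecast. The size of the gap among study leavers cannot be computed from the documents. The 30-day medication definition and the missing medication check at EOS are small inconsistencies of the same kind. They add nothing to the TEAE under-count.

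**What to change.** - **Table 2 and footnote b:** for subjects treated to Week 52, schedule EOS 28 days after the last dose with a window of 0 to +7 days. EOS then falls 28 to 35 days after the last dose.
- **9.5.1.5.1:** replace the reference to the last Treatment Phase visit with a statement that all AEs are collected to 28 days after the last dose, to match 9.7.1.8.2. Add a telephone AE check at that point for subjects who leave the study.
- **Concomitant medication:** mark a check at EOS in Table 2 and reconcile the 30 days in 9.7.1.5 with the 28-day rules elsewhere.

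The cost is a few text edits, one call per study leaver, and a later EOS visit for some completers. The latest permitted EOS moves from 392 + 7 = 399 to 371 + 35 = 406 days after Day 1, which is one week.
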